11. STATISTICS

11.1. General

Before database lock, a statistical analysis plan (SAP) will be issued as a separate document, providing detailed methods for the analyses outlined below. Any deviations from the planned analyses will be described and justified in the final clinical study report.

For descriptive summaries, continuous variables will be summarized with N (ie, sample size), mean, standard deviation, median, 25th percentile (Q1), 75th percentile (Q3), minimum (min), and maximum (max), and discrete variables will be summarized with frequencies and percentages. Summary results will be displayed by treatment group.

11.2. Primary Objective Estimand

The primary objective of this study is to determine the safety and efficacy of the combination of plamotamab, tafasitamab, and lenalidomide compared to tafasitamab and lenalidomide in adult subjects with relapsed or refractory diffuse large B-cell lymphoma using Lugano 2014 criteria ([Cheson, 2014](#)). The attributes for the estimand for the primary objective are outlined in [Table 20](#).

Table 20: Primary Objective Estimand

Primary Estimand				
Population	Variable	Summary Measure	Treatment	Potential Intercurrent Events
Intent-to-treat: all randomized subjects in Part 2	Blinded Independent Review Committee assessment of PFS, defined as the time from randomization to first documentation of progressive disease or death, whichever comes first.	Hazard ratio based on Cox regression model stratified by IPI risk score at baseline, number of lines of prior therapy, and primary refractory. KM estimates for median, Q1 and Q3. Stratified log-rank test for treatment effect.	Plamotamab, tafasitamab, and lenalidomide versus tafasitamab, and lenalidomide	Discontinuation of treatment(s), start of a new anti-cancer therapy, including transplant and missing two or more tumor assessments. Treatment policy estimand will apply for intercurrent events.

IPI = international prognostic index; PFS = progression-free survival.

11.3. Sample Size and Power

11.3.1. Progression-Free Survival

PFS as assessed by the BIRC is the primary endpoint for Part 2 of this study. For determination of the sample size, it is assumed that triple combination treatment could improve the median PFS from 12 months (under treatment with tafasitamab + lenalidomide (Duell, 2021) to 23.5 months under the triple combination treatment (plamotamab + tafasitamab + lenalidomide), corresponding to a hazard ratio (HR) of 0.51 with all randomized subjects (it is estimated that 90% of subjects will be central pathologically confirmed as DLBCL).

The log rank test has 90% power with the sample size of 200 (93 events) to preserve the type-I error of 0.025 (one-sided). A loss to follow-up rate of 1.5%/month was assumed for sample size calculations.

Subjects will be randomized 1:1, stratified by IPI risk score at baseline (3 to 5 versus 0 to 2), number of lines of prior therapy (1 versus ≥ 2), and primary refractory (yes versus no). A maximum of 36 primary refractory subjects may be enrolled into the sample size of 200.

Enrollment of 200 subjects is estimated to require 27 months with minimum follow-up time of 6 months. The primary efficacy analysis will occur when 93 PFS events per independent review have been observed. Efficacy boundaries and estimated timing for the analysis is displayed in [Table 21](#).

Table 21: Efficacy Boundaries and Properties for Progression-Free Survival Analyses

Analysis	Value	Efficacy
Final	Z	1.9600
N: 200	p (1-sided)	0.0250
Events: 93	HR at bound	0.6659
Month: 33	P(Cross) if HR = 1	0.0250
	P(Cross) if HR = 0.51	0.9000

p (1-sided) is the nominal α for testing.

HR at bound is the approximate HR required to reach an efficacy bound

P(Cross if HR = 1) is the probability of crossing a bound under the null hypothesis

P(Cross if HR = 0.5) is the probability of crossing a bound under the alternative hypothesis

HR = hazard ratio.

An interim analysis for OS at the time of final PFS analysis will be implemented using the group sequential design in addition to the final OS analysis. [Table 22](#) provides the timing of PFS and OS analysis.

Table 22: Summary of Interim and Final Analyses Strategy

Analyses	Key Endpoints	Timing	Estimated Time after First Subject Randomized	Primary Purpose of Analysis
PFS Final OS IA1	PFS ORR OS TTF	93 PFS event and approx. 50 OS events (65% of expected total OS events) have been observed	Approx. 33 months	
 Final analyses for PFS, ORR, and TTF Interim OS analyses
Final OS Analysis	OS	When approx. 76 OS events have been observed	Approx. 51 months	
 Final OS analyses

ORR = objective response rate; OS = overall survival; PFS = progression-free survival; TTF = time to treatment failure.

11.3.2. Overall Survival

Overall survival will be assessed in the randomized population (Part 2). The one-sided α level for testing OS is at 0.025. It is assumed that the median OS for the Part 2 Arm B is 34 months and that Part 2 Arm A will have 40% improvement from Arm B (ie, median OS = 56.6 months, HR = 0.60). In addition, assuming completion of enrollment in 27 months, a minimum follow-up time of 24 months, and an OS censoring rate (dropout rate) of approximately 1% per month, the study will result a statistical significance with 60% of power. Once 65% of the information (death events) is

available, an interim analysis for OS is planned. Superiority analyses will be performed during the interim and final analyses. [Table 23](#) provides more details.

Table 23: Efficacy Boundaries and Properties for Overall Survival Analyses

Analysis	Value	Efficacy
IA 1: 65%*	Z	2.5469
N: 200	p (1-sided)	0.0054
Events: 50	HR at bound	0.4833
Month: 33.8	P(Cross) if HR=1	0.0054
	P(Cross) if HR=0.6	0.2263
Final	Z	1.9896
N: 200	p (1-sided)	0.0233
Events: 76	HR at bound	0.6326
Month: 51	P(Cross) if HR = 1	0.0250
	P(Cross) if HR = 0.6	0.6000

*Expected percentage of events with respect to the number of events expected at the final analysis.
 p (1-sided) is the nominal α for testing.
 HR at bound is the approximate HR required to reach an efficacy bound.
 P(Cross if HR = 1) is the probability of crossing a bound under the null hypothesis
 P(Cross if HR = 0.6) is the probability of crossing a bound under the alternative hypothesis
 HR = hazard ratio; IA = interim analysis
 Efficacy bounds derived using a Lan-DeMets O'Brien-Fleming approximation spending function.

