11.3.3. Objective Response Rate

The one-sided α level for testing ORR is at 0.025. It is assumed the ORR for Part 2 Arm B is 60% and ORR for Part 2 Arm A is 78%. 100 subjects per arm will provide 80% power for statistical significance at 0.025.

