11.3.4. Statistical Testing Sequence

The following secondary endpoints will be tested sequentially in the following order, if the test for the primary endpoint is positive:

1. ORR by BIRC per Lugano 2014 criteria ([Cheson, 2014](#))
2. OS

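### The 60% power for OS (and 80% for ORR) is the power of each endpoint tested alone; within the plan's testing sequence it is lower, about 43% for OS if the endpoints are independent

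*Protocol*

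**What the plan says.** Protocol section 11.3.2 sets the OS test at the full one-sided level ("The one-sided α level for testing OS is at 0.025") and assumes "median OS = 56.6 months, HR = 0.60". It concludes that "the study will result a statistical significance with 60% of power". Table 23 gives bounds of Z = 2.5469 at 50 deaths and 1.9896 at 76 deaths, and a cumulative crossing probability of 0.6000 at HR 0.6. Its footnote reads "Efficacy bounds derived using a Lan-DeMets O'Brien-Fleming approximation spending function".

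Section 11.3.3 does the same for response: with 60% against 78%, "100 subjects per arm will provide 80% power for statistical significance at 0.025".

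Section 11.3.4 then makes these tests conditional: "The following secondary endpoints will be tested sequentially in the following order, if the test for the primary endpoint is positive". The order is ORR by BIRC, then OS, then TTF. The synopsis repeats it.

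Neither document labels the 60% or the 80% as applying to an endpoint tested alone, gives a power within the sequence, or gives a correlation among PFS, ORR and OS. SAP sections 5.1 and 5.2 repeat the PFS sample size and the timing of the OS analyses but add no OS power.

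**The concern.** The fixed sequence is what lets PFS, ORR and OS each be tested at the full one-sided 0.025. Its cost is that a failure at PFS or ORR stops the sequence before OS. Section 11.3.2 speaks of what the study will achieve, yet the figure describes an OS test that is always carried out. The interim value of 0.2263 in Table 23 is subject to the same gates.

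At stake is how the sponsor and reviewers judge the prospect of an OS claim. The protocol allows the Part 2 sample size to be adjusted before randomization starts (sections 4.1.2 and 4.4). A team weighing that choice on 60% for OS and 80% for ORR would be using figures that leave out the testing order.

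**Working it through.** **Inputs, all from the protocol.**
- PFS: HR 0.51, 93 events, one-sided 0.025, 90% power (11.3.1).
- ORR: 60% against 78%, 100 per arm, one-sided 0.025, 80% power (11.3.3).
- OS: HR 0.60, bounds 2.5469 and 1.9896 (11.3.2, Table 23). Table 22 times the interim when "approx. 50 OS events (65% of expected total OS events) have been observed" and the final "When approx. 76 OS events have been observed".
- Order: PFS, ORR, OS, TTF (11.3.4).

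**Step 1. Reproduce the plan's own figures.**

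*OS alone.* With 1:1 allocation the mean of the log-rank Z is |ln HR| x sqrt(events)/2, and |ln 0.60| = 0.5108.
- Interim: 0.5108 x sqrt(50)/2 = 1.806. P(Z > 2.5469) = 1 - Φ(0.741) = 0.229 (plan: 0.2263; 49.4 deaths, which is 65% of 76, gives 0.226).
- Final: 0.5108 x sqrt(76)/2 = 2.227.
- Correlation between the two looks: sqrt(50/76) = 0.811.
- Probability of crossing either bound: 0.5995 at HR 0.60 and 0.0250 at HR 1.

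So 60% is right as a marginal figure.

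*PFS.* |ln 0.51| x sqrt(93)/2 - 1.96 = 3.247 - 1.96 = 1.287, and Φ(1.287) = 0.901. The stated 90% reproduces.

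*ORR.* The difference is 0.18. The null standard error is sqrt(2 x 0.69 x 0.31/100) = 0.0654. The alternative standard error is sqrt((0.60 x 0.40 + 0.78 x 0.22)/100) = 0.0642.
- Pooled test: Φ((0.18 - 1.96 x 0.0654)/0.0642) = Φ(0.807) = 0.790.
- Unpooled test: Φ(0.18/0.0642 - 1.96) = 0.801.

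The stated 80% holds to within about a point.

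**Step 2. Apply the sequence under independence.**
- P(PFS and ORR both significant) = 0.90 x 0.80 = 0.72, or 0.90 x 0.79 = 0.71.
- P(PFS, ORR and OS all significant) = 0.90 x 0.80 x 0.60 = 0.432, or 0.90 x 0.79 x 0.60 = 0.427.

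**Step 3. Limits that hold for any correlation.** A joint probability cannot exceed its smallest component. The ceiling is therefore 0.60 for OS and 0.79-0.80 for ORR.

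**Step 4. Sensitivity to an assumed common positive correlation.** The documents give none, so these rows are illustrations. Two scales were used:
- On test statistics: a multivariate normal model, either with both OS looks (2,000,000 draws; the final OS statistic's correlation with PFS and ORR is the assumed value times 0.811) or with a single OS look.
- On patient outcomes: simulated trials with the plan's medians, response rates, accrual, dropout and bounds (4,000 per setting, standard error about 0.8 points). Where a range is shown, two separate simulations differed.

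| Assumed correlation | OS in sequence, test statistics, two looks | Same, single look | OS in sequence, patient outcomes | PFS and ORR both significant, test statistics |
|---|---|---|---|---|
| 0 | 0.432 | 0.432 | 0.42-0.43 | 0.720 |
| 0.3 | 0.478 | 0.486 | 0.45 | 0.737 |
| 0.5 | 0.508 | 0.522 | 0.48-0.49 | 0.751 |
| 0.7 | 0.538 | 0.558 | 0.51 | 0.769 |
| 0.9 | 0.568 | 0.593 | 0.54 | 0.791 |

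On the patient-outcome scale, P(PFS and ORR both significant) ran from 0.71 to 0.76.

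**Step 5. Event count.** The synopsis, protocol section 4.1.2 and SAP section 3.1.2 give 89 PFS events instead of 93. With 89, PFS power is Φ(0.6733 x sqrt(89)/2 - 1.96) = Φ(1.216) = 0.888, and the product is 0.888 x 0.80 x 0.60 = 0.426. The conclusion does not change.

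**The case against.** The strongest reply is that nothing is miscalculated. Table 23 defines its entry as a boundary-crossing probability, and that probability is correct. Quoting each endpoint's power at its own alpha is ordinary in a fixed-sequence design, and the sequence stands under the same main heading, 11.3. This stands for the table. It does not rescue the sentence in 11.3.2, which attributes 60% to the study without qualification.

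A second reply is that any in-sequence figure above independence rests on a correlation the reviewer supplies. This also stands. A reader might take 54%, the value at a patient-level correlation of 0.9, as an upper limit for OS. It is not one: the same nominal correlation placed on the test statistics gives 57-59%, and the only hard ceiling is 60%. Nor is 43% a likely value. Deaths count as PFS events, so PFS and OS share information and some positive correlation is to be expected. Independence is a reference point that needs no outside input.

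Third, the consequence is limited. The 200 subjects are sized on PFS, and 60% already discloses modest OS power. The protocol was to be revised before Part 2. The SAP (sections 1, 4.1 and 7) records early termination with 3 subjects and no efficacy analyses. All of that is true. It reduces the weight of the point but does not make an unqualified 60% true of the stated sequence.

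**Conclusion.** The point holds as a labelling and reporting defect. The 60% for OS and the 80% for ORR are correct marginal powers, presented without saying so in a plan that tests both behind gates. Within the sequence, OS power is about 43% under independence, 17 points below the stated figure. At an assumed correlation of 0.5 it is about 48-52%, depending on whether the correlation is placed on patient outcomes or on test statistics, and it cannot exceed 60%. ORR power within the sequence is about 71-72% under independence, with a ceiling of about 79-80%. These figures take the plan's effect sizes and event counts as given.

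A reader might infer that the OS calculation is wrong, or that the sequence fails to control type I error. The documents support neither: the bounds reproduce, with a one-sided error of 0.0250, and the order of testing is not in question. A reader might also infer that an OS claim is less likely than not. That is so under independence, but at an assumed correlation of 0.5 the answer already depends on the scale chosen.

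**What to change.** - **Section 11.3.2 and Table 23:** state that 60% (and the interim 0.2263) is the power of OS tested alone. Add that power within the 11.3.4 sequence is about 43% if PFS, ORR and OS are independent (0.90 x 0.80 x 0.60), higher with positive correlation (for example about 48-52% at an assumed 0.5, naming the scale), and at most 60%.
- **Section 11.3.3:** label 80% as marginal. Add about 71-72% within the sequence under independence, rising with correlation to a ceiling of about 79-80%.
- **Both places:** mark every value above independence as resting on an assumed correlation that the documents do not give.

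The cost is a few sentences and less favourable stated figures. No test, alpha level, bound or sample size changes. Because the study stopped after 3 subjects, the correction matters for the record and for any reuse of the design, not for a result of this trial.

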11.3.3. Objective Response Rate

The one-sided α level for testing ORR is at 0.025. It is assumed the ORR for Part 2 Arm B is 60% and ORR for Part 2 Arm A is 78%. 100 subjects per arm will provide 80% power for statistical significance at 0.025.

11.3.4. Statistical Testing Sequence

The following secondary endpoints will be tested sequentially in the following order, if the test for the primary endpoint is positive:

1. ORR by BIRC per Lugano 2014 criteria ([Cheson, 2014](#))
2. OS
3. TTF

Other secondary efficacy endpoints will be assessed, including:

- PFS, as assessed by Investigator
- ORR by Investigator
- DOR among subjects achieving an objective response
- DOR among subjects achieving a CR

11.4. Independent Data Monitoring Committee

A separate charter will describe the membership and operation of the IDMC. In Part 2, accumulating safety data will be reviewed by the IDMC periodically, as detailed in [Section 4.9](#).

11.5. Analysis Sets

The following populations will be used for analysis as defined below:

- **Enrolled Analysis Set:** All subjects who signs the informed consent form, is determined to be eligible, and receives the Day –8 tafasitamab dose
- **Safety Run-in Analysis Set:** All subjects who are enrolled in Part 1 of the study and receive at least 1 dose each of plamotamab, tafasitamab, and lenalidomide
- **Randomized (Intent-to-Treat) Analysis Set:** All subjects who are randomized into Part 2 of the study
- **Randomized Safety Analysis Set:** All subjects who are randomized into Part 2 of the study and receive at least 1 dose of plamotamab, tafasitamab, or lenalidomide
- **Pharmacodynamic Analysis Set (s):** All subjects who are enrolled in the study, receive at least 1 dose of study therapy, and have at least 1 set of pre- and post-infusion pharmacodynamic data available for analysis — defined independently for Parts 1 and 2.
- **PK Analysis Set (s):** All subjects who are enrolled in the study, receive at least 1 dose of study therapy, and have at least 1 set of pre- and post-infusion PK data available for analysis — defined independently for Part 1, Arm A, and Arm B.
- **Plamotamab Treated Analysis Set:** All subjects treated with any amount of plamotamab in Part 1 or Part 2.

11.6. Key Subgroups

Key subgroups include:

- IPI risk score at baseline (3 to 5 versus 0 to 2)

- Primary refractory (yes versus no)
- Number of lines of prior therapy (1 versus ≥ 2)

11.7. Subject Characteristics and Disposition

The SAP will define analysis parameters for the study and takes precedence over this protocol section.

Demographic and baseline characteristics will be summarized, as will disease-related characteristics (including any available genetic data), prior anti-cancer therapies, and relevant supportive care therapies.

A summary of subject disposition will include the following, by Part and by Arm:

- Number of subjects enrolled
- Number of subjects who received each study treatment
- Number of subjects who terminated treatment earlier and reason for early discontinuation of treatment
- Number of subjects who complete the study follow-up period
- Number of subjects who terminated study earlier and reasons for early study terminations

11.8. Safety Analysis

Safety Analysis will be performed with Safety Analysis Set. Safety variables will include AEs/SAEs, vital signs, PE findings, ECGs, laboratory values, medical history, and concomitant medications, which will be summarized by Part and by Arm.

The extent of exposure to plamotamab and tafasitamab will be summarized based on the number of infusions administered and the number of treatment cycles completed, as well as the total dose received. Lenalidomide exposure will be summarized similarly, based on number of doses taken.

Additional summaries of drug exposure will be provided based on the PK parameters described in [Section 11.10](#).

AEs will be coded using the latest version of Medical Dictionary for Regulatory Activities (MedDRA). The verbatim term recorded by the Investigator will be mapped to System Organ Class (SOC) and Preferred Term using MedDRA.

TEAEs are defined as events with onset dates on or after the start of study treatment or events that are present before the first infusion of study treatment and subsequently worsen in severity.

AE-related endpoints include:

- Treatment-emergent AEs
- Treatment-emergent SAEs
- Adverse reactions
- Serious adverse reactions
- Treatment-emergent AEs by severity, as defined by NCI-CTCAE Version 5.0
- Treatment-emergent AEs resulting in the permanent discontinuation of plamotamab

All AE-related endpoints will be summarized by SOC and preferred term. At each level of summation, subjects will be counted once, under the greatest severity and strongest study-drug relationship.

The hematology, chemistry, and other laboratory values and change from baseline values will be summarized descriptively for each scheduled assessment time point and grouped by dosing cohort. The baseline value for each laboratory value is defined as the last assessment performed on or prior to the date of first dose of study treatment. The frequencies of Grade 3 and 4 hematologic AEs (including neutropenia, thrombocytopenia, and anemia) will be reported. The toxicity grades for laboratory tests will be based on NCI-CTCAE Version 5.0 ([NCI-CTCAE, 2017](#)) criteria. The use of blood transfusions (platelets, RBCs) and/or growth factor support will be reported. Similar analyses will be done for chemistry tests (including liver and renal function tests). Subject listings of all laboratory data collected during the study will be presented. Laboratory values outside normal limits will be identified in the subject listings and will include flags for high and low values.

Vital sign results (blood pressure, heart rate, respirations, temperature, and blood oxygen saturation by continuous pulse oximetry) will be summarized descriptively for each scheduled time point. The baseline value for each vital sign measurement is defined as the last assessment performed most recently prior to the first dose of study treatment, and any change from these baseline values will be reviewed. The change of vital signs values from preinfusion will be summarized for each postinfusion point. Preinfusion assessments are defined as last vital assessment prior to the same infusion. Subject listings of all vital data collected during the study will be presented.

ECGs values and change from baseline values will be summarized descriptively for each scheduled time point. Subject listings of all ECG data collected during the study will be presented.

Additional analysis will be performed for AEs of CRS. These will include analyses of time to onset, duration, severity, and associations with laboratory cytokine measurements and missed or delayed doses (ie, CRS may be associated with longer intervals between doses). Graphical summaries will illustrate the timing relative to dosing, the severity of CRS events and cytokine levels.

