2.4. Human Experience with Plamotamab

Plamotamab is being studied in a Phase 1 study, XmAb13676-01 (A Phase 1 Multidose Study to Evaluate the Safety and Tolerability of XmAb[®]13676 in Patients with CD20-Expressing Hematologic Malignancies). As of 18 August 2021, a total of 96 subjects have been treated with plamotamab in the XmAb13676 01 study at weight-based dose levels of 0.7 to 360 µg/kg and flat dose levels of 0.8 to 50 mg. Of those 96 subjects, 80 were in the NHL group and 16 were in the CLL group. Adverse events (AEs) have been reported in 100% of the 80 NHL subjects. The most frequent AEs (>20%) in the NHL group were cytokine release syndrome (51/80, 63.8%), pyrexia (43/80, 53.8%), anemia (34/80, 42.5%), fatigue (24/80, 30.0%), nausea (21/80, 26.3%), diarrhea and cough (20/80, 25.0%), constipation (19/80, 23.8%), chills, headache, hypokalemia, and thrombocytopenia, (18/80, 22.5%), asthenia, dizziness, dyspnoea, hypotension, and neutropenia (17/80, 21.3%). Cytokine release syndrome (CRS), a predicted toxicity for this class of drugs, has occurred in subjects treated at 7.5, 10, 20, 25, 45, 50, 80, 125, 170, 250 µg/kg and at 0.8, 2, 20, 35 mg; however, CRS has not yet been seen at the highest dose levels of 360 µg/kg and 50 mg, in this study. The pattern of these events has differed in the NHL versus the CLL cohorts in this study.

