4.1.1. Part 1: Single-Arm, Safety Run-In

Part 1 consists of a single-arm evaluation of the safety of the triple combination of plamotamab combined with tafasitamab plus lenalidomide in at least 40 subjects in 2 cohorts of a minimum of 20 subjects per cohort:

- Cohort 1A treats subjects with the triple combination at plamotamab dose level –1 ([Table 3](#)).
- Cohort 1B commences enrollment after the Cohort 1A completes enrollment. Cohort 1B treats subjects with the triple combination at plamotamab dose level 1 ([Table 3](#)).
- An initial safety evaluation is conducted after all subjects in Cohorts 1A and 1B either receive treatment, at a minimum, through C4D28 or are discontinued prior to C4D28 due to an AE or progressive disease.

After the initial safety evaluation of both Cohorts 1A and 1B, the pharmacologically optimal dose of plamotamab (dose level -1 or dose level 1) with an acceptable safety profile will be advanced to the randomized (Part 2) portion of the study.

Table 3: Cohort 1A and Cohort 1B Plamotamab Dosing Regimen

Cohort	Dose Level	Cycle 1 Day 1 (Priming Dose)	Cycle 1 Day 8	Cycle 1 Day 15	Cycle 1 Day 22	Cycle 2 Day 1	Cycle 2 Days 1, 8, 15, and 22	Cycle 3 and Subsequent Q2W Dosing
1A	-1	0.8 mg	2 mg	20 mg	20 mg	20 mg	20 mg	20 mg
1B	1	0.8 mg	2 mg	20 mg	35 mg	50 mg	50 mg	50 mg

Q2W = every 2 weeks.

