4.2. Endpoints

4.2.1. Primary Endpoints

The primary endpoint of the study is

- For Part 1, safety as measured by incidence of CRS and TEAEs; and
- For Part 2, PFS, defined as the time from randomization to first documentation of progressive disease or death, whichever comes first, as assessed by the BIRC using Lugano 2014 criteria.

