4.3.1. Part 1: Single-Arm, Safety Run-In

Part 1 is a single-arm, two-cohort, safety run-in intended to establish the safety of the combination of plamotamab, tafasitamab, and lenalidomide.

Treatment consists of the combination of plamotamab, tafasitamab, and lenalidomide administered in 28-day cycles, with 2 priming doses of tafasitamab before Cycle 1. Plamotamab and tafasitamab can be administered until disease progression, unacceptable toxicity, or discontinuation for any other reason, whichever comes first; however, lenalidomide can be given for only up to a total of 12 cycles. Tafasitamab and plamotamab must not be administered simultaneously. On days when both tafasitamab and plamotamab are given, the tafasitamab should be given first followed by plamotamab. It is recommended that the infusions are separated by at least 2 hours.

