4.6.1. Cytokine Release Syndrome

The ASTCT defines CRS as “a supraphysiologic response following any immune therapy that results in the activation or engagement of endogenous or infused T cells and/or other immune effector cells. Symptoms can be progressive, must include fever at the onset, and may include hypotension, capillary leak (hypoxia), and end organ dysfunction” (Lee, 2019).

CRS can present with a variety of symptoms ranging from mild, flu-like symptoms to severe life-threatening manifestations of the inflammatory response. Mild symptoms of CRS include fever, fatigue, headache, rash, arthralgia, and myalgia. More severe cases are characterized by hypotension as well as high fever and can progress to an uncontrolled systemic inflammatory response with vasopressor-requiring circulatory shock, vascular leakage, disseminated intravascular coagulation, and multi-organ system failure (Shimabukuro-Vornhagen, 2018). CRS is more likely to occur after the first dose of plamotamab than subsequent doses, tends to begin somewhat later than hypersensitivity reactions, and is more likely to be associated with hepatic and neurologic complications. Plamotamab associated CRS Symptoms observed in the Phase 1 study include:

- Aphasia or word-finding difficulty
- Arthralgia
- Confusion/mental status changes/delirium
- Serum creatinine increase
- Diaphoresis
- Dizziness
- Dyspnea
- Fatigue (asthenia, lethargy, malaise)
- Fever
- Gait disturbance/dysmetria
- Headache
- Hypotension/hypertension
- Hypoxia
- Myalgia
- Nausea/vomiting
- Rigors/chills
- Tachycardia
- Tachypnea
- Seizures
- Transaminitis/hyperbilirubinaemia
- Tremor

CRS toxicity is defined using the ASTCT CRS Consensus Grading (Lee, 2019). See Table 4 for these definitions.

Table 4: American Society for Transplantation and Cellular Therapy Cytokine Release Syndrome Consensus Grading

CRS Parameter	Grade 1	Grade 2	Grade 3	Grade 4
Fever ^a	Temperature ≥ 38 °C	Temperature ≥ 38 °C	Temperature ≥ 38 °C	Temperature ≥ 38 °C
		With		
Hypotension	None	Not requiring vasopressors	Requiring a vasopressor with or without vasopressin	Requiring multiple vasopressors (excluding vasopressin)
		And/or ^b		
Hypoxia	None	Requiring low-flow nasal cannula ^c or blow-by	Requiring high-flow nasal cannula ^c , facemask, nonrebreather mask, or Venturi mask	Requiring positive pressure (eg, CPAP, BiPAP, intubation and mechanical ventilation)

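### Part 1 must choose between two plamotamab dose levels, but no AE or CRS incidence is specified by cohort or from C1D22, when the regimens first differ

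*Protocol*

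**What the plan says.** **Decision.** After the safety evaluation of both cohorts, "the pharmacologically optimal dose of plamotamab (dose level -1 or dose level 1) with an acceptable safety profile will be advanced" to Part 2 (protocol 4.1.1).

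**Endpoint.** "For Part 1, safety as measured by incidence of CRS and TEAEs" (protocol 4.2.1; repeated in SAP 2.4.1).

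**Structure.** "Part 1 is a single-arm, two-cohort, safety run-in" (protocol 4.3.1), run "in at least 40 subjects in 2 cohorts of a minimum of 20 subjects per cohort" (4.1.1).

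**Grouping.** Section 11.8 gives the safety variables as "AEs/SAEs, vital signs, PE findings, ECGs, laboratory values, medical history, and concomitant medications, which will be summarized by Part and by Arm". It says that a subject counts once at each level of summation, and that TEAEs run from the start of study treatment. Later in 11.8, laboratory values are to be grouped by dosing cohort. Section 11.1 says that results are displayed by treatment group, without saying whether a cohort is one. Section 4.8 says that the sponsor will assess data from both cohorts, without giving a method.

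**Doses.** Table 3 gives both cohorts 0.8, 2 and 20 mg on C1D1, C1D8 and C1D15. They first differ on C1D22 (20 mg against 35 mg), and then from C2D1 (20 mg against 50 mg).

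**Phase 1 experience.** "CRS is more likely to occur after the first dose of plamotamab than subsequent doses" (4.6.1). None had been seen at 50 mg (2.4), and none occurred after two-weekly dosing began in the flat-dose cohort (2.4.3). "Adverse events (AEs) have been reported in 100% of the 80 NHL subjects" (2.4).

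**The concern.** The purpose of Part 1 is to choose a dose, so its safety summary has to show whether the higher level is more toxic. Two features work against that.

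1. Read literally, one column for a single-arm Part 1 gives no contrast between the dose levels at all.
2. Splitting by cohort would not be enough. A subject who had CRS during the shared step-up already counts as a case, so recurrence at the higher dose adds nothing to incidence. The shared doses therefore dilute any real difference.

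Any-TEAE incidence is little help, because it was 100% in Phase 1. At stake is a safety comparison that may look alike at both levels, beside an exposure prediction that already separates them: 52% of subjects at 20 mg and 83% at 50 mg exceed 650 ng/mL (2.4.3).

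**Working it through.** The documents give no power, threshold or decision rule for Part 1, so there is no design figure to reproduce. The Phase 1 rates used here do check: 8/14 = 57.1% and 51/80 = 63.75% (stated as 63.8%).

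**1. How much of the window is shared.** The minimum window is Day -8 to C4D28.
- Shared days: 8 (Day -8 to Day -1) + 21 (C1D1 to C1D21) = 29.
- Total days: 8 + 4 × 28 = 120. Shared fraction: 29/120 = 24%.
- Plamotamab doses through Cycle 4: 4 + 4 + 2 + 2 = 12 if Cycle 2 is weekly (Table 3), or 4 + 2 + 2 + 2 = 10 if it is two-weekly (text of 7.1.1). Three are shared, that is 25-30%. The two schedules conflict and must be reconciled.
- Cumulative dose, 12-dose schedule: 1A 42.8 + 8 × 20 = 202.8 mg; 1B 57.8 + 8 × 50 = 457.8 mg. With 10 doses: 162.8 and 357.8 mg.

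The shared period is thus a minority of the window, but it holds the doses at which most CRS is expected.

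**2. Dilution of CRS incidence.** Let c be CRS incidence during the shared doses and r the incidence from C1D22, taken as independent. Then overall incidence = c + (1 - c) × r, and a later gap between cohorts shrinks by the factor (1 - c).

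Inputs:
- n = 20 per cohort, all assumed to reach C1D22.
- r in 1A = 5%; r in 1B = 30% or 15%. Both are assumptions; the documents give no such rates.
- c from 20% to 64%. The values 57% (flat-dose cohort) and 64% (all NHL subjects) are all-dose Phase 1 rates, so they are high values for c. Lower values allow for the tafasitamab run-in, which 2.4.3 says could mitigate CRS.

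Example with c = 57%: 1A 0.57 + 0.43 × 0.05 = 59.15%; 1B 0.57 + 0.43 × 0.30 = 69.9%. A 25-point gap becomes 0.43 × 25 = 10.75 points. Pooled, the display would be a single rate of (59.15 + 69.9)/2 = 64.5%.

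The chance that 1B shows no excess is the exact binomial sum P(X_1B ≤ X_1A), with 20 subjects in each cohort:

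| c | 1A vs 1B overall (r in 1B = 30%) | No excess | 1A vs 1B overall (r in 1B = 15%) | No excess |
|---|---|---|---|---|
| 20% | 24.0% vs 44.0% | 12% | 24.0% vs 32.0% | 35% |
| 40% | 43.0% vs 58.0% | 21% | 43.0% vs 49.0% | 41% |
| 57% | 59.2% vs 69.9% | 29% | 59.2% vs 63.5% | 45% |
| 64% | 65.8% vs 74.8% | 32% | 65.8% vs 69.4% | 47% |
| Events from C1D22 only | 5% vs 30% | 2% | 5% vs 15% | 21% |

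As a gauge of separation only, one-sided 10% Fisher power at c = 57% is 19% overall against 70% from C1D22 when r in 1B is 30%. When it is 15%, power is 9% against 20%.

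**3. Any-TEAE incidence.** With 80 of 80 in Phase 1, the exact lower 95% limit is 0.025^(1/80) = 95.5%. Both cohorts would show 20/20 with probability 0.955^40 = 16% at that limit, 0.988^40 = 62% at an assumed 98.8%, and 100% at a true rate of 100%.

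**4. Precision.** An observed 11/20 = 55% has an exact 95% CI of 32-77%. With 20 per cohort and a two-sided 5% test, 80% power needs a gap of about 40 points (10% against 50%).

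**The case against.** **Pooling is not a stated plan.** A reader might infer that the plan merges the two cohorts for the dose decision. The documents do not say so. The sentence in 11.8 that says by Part and by Arm includes laboratory values, which the same section then groups by dosing cohort, so the phrase does not exclude cohort columns. Sections 11.1 and 4.8 also point towards some review by cohort. This stands: the gap is that AE and CRS tables by cohort are not specified.

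**The window is not an identical-dose period.** A reader might also infer that the endpoint is counted only while doses are the same. About 76% of the minimum window is at different doses, and by C4D28 Cohort 1B has had more than twice the cumulative dose of 1A. This stands too. The dilution comes from where CRS falls, not from the length of the shared period.

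**Other summaries can separate the levels.** Section 11.8 also plans TEAEs by severity and by preferred term, SAEs, discontinuations of plamotamab, and CRS timing and severity. The ceiling affects only the any-TEAE row. This is correct, but apart from laboratory data none of these is specified by cohort.

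**The size rests on assumed rates.** Later CRS of 30% in 1B is high beside Phase 1, where none was seen at 50 mg, although CRS did occur at 35 mg. With 15% the gain is modest, and power from C1D22 is only about 20%. The protocol states no test between cohorts, so low power is not a failed objective. The ranges above therefore matter more than any single figure.

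**Consequences are limited.** Section 4.1.1 requires an acceptable safety profile, and 4.1.2 requires a protocol revision with justification before Part 2. Nothing shows that the choice would have rested on exposure alone.

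**Conclusion.** The concern holds as a gap in specification with a measurable effect. Part 1 must choose a dose level, yet no AE or CRS incidence is specified by cohort, and overall CRS incidence carries the shared step-up. Over step-up CRS of 20-64%, a later difference of 5% against 30% would show as no excess in 1B about 12-32% of the time on overall incidence, against 2% from C1D22. For 5% against 15% the figures are about 35-47% and 21%. They rest on 20 subjects per cohort, independence of early and late CRS, and later rates that the documents do not supply.

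It does not follow that the cohorts would have been pooled in practice, or that the safety data as a whole could not tell the dose levels apart. Even after the change, 20 per cohort supports only a descriptive comparison. With 3 subjects enrolled and listings only in the SAP (sections 1, 4.1 and 7), no reported result is affected.

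**What to change.** In section 11.8:

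- State that AE and CRS summaries are by cohort (1A, 1B) in Part 1 and by arm in Part 2.
- Add, by cohort with exact 95% confidence intervals, CRS (any grade and Grade ≥ 3) and Grade ≥ 3 TEAEs for events starting on or after the C1D22 plamotamab dose. Count them regardless of earlier events, among subjects who receive that dose.
- Report earlier step-up events separately, pooled over the cohorts.
- Keep overall incidence by cohort as a descriptive table.

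The cost is a few sentences and a few tables. No new data are needed, because AE onset dates and times (10.3) and administration times (7.3) are already recorded. The downside is that subjects who stop before C1D22 leave the denominator of the later comparison, but they remain in the overall tables. For the terminated study the listings need no change; the wording matters if the design is reused.
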